Official Title: Contraceptive Awareness and Reproductive Education

STUDY PROTOCOL AND STATISTICAL ANALYSIS PLAN

The University of Rhode Island
Date of Document: August 2023

NCT01627574

Study Overview

Nearly 5% of reproductive-age women experience unintended pregnancy each year and this rate is significantly higher than in other developed countries.¹ More than half of all new sexually transmitted diseases (STDs) reported in 2020 were among young people ages 15-24 years old, and among sexually active young women, only 47% reported using a condom during their last intercourse.² Unintended pregnancies are highest among low-income women, women ages 15-24 years and women of color.¹ Youth in justice, mental health and alternative school settings all appear to be at increased risk for unintended pregnancy and STIs,³⁻⁵ and this may be related to the overlap in youth entering and exiting these systems.⁶⁻⁸ Although young women in alternative school, justice and mental health settings are at increased risk to engage in sexual risk-taking, relatively few interventions have been developed for them.

Behavioral intervention may be effective in reducing sexual risk and should include information on sexually transmitted infections (STIs), motivating commitment to safer sex, training in condom use and partner communication, and problem-solving.⁹ Motivational Interviewing (MI) is well-suited to reduce risky sexual behaviors in youth as it engages, is directive, elicits youth motivations for reducing risk, and attends to creating a change plan as appropriate; however, further work is needed to refine and test MI for sexual risk-taking behaviors.¹⁰ Meta-analyses¹¹⁻¹² indicate MI may be particularly useful for minoritized populations; however, as a treatment for risky sex, more study is needed, including addressing the impact of poverty.¹⁰

Study Objectives

Aims: To evaluate in a randomized clinical trial the degree to which Computer Assisted Motivational Interviewing (CAMI) compared to Didactic Educational Counseling (DEC) will:

1. **Increase the initiation of highly effective contraceptives in a high-risk juvenile population.** Hypothesis: CAMI will increase the initiation of highly effective contraceptives in girls more than DEC. The **primary outcome** is initiation of a highly effective (e.g., hormonal) contraceptive method. This will be measured using calendar-assisted self-report.

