Participants in the DEC group did not receive any personalized feedback and did not create a collaborative SAFE plan. Although there is overlap in some information presented in the two groups, the style and spirit of CAMI is different from DEC in that CAMI is based on Readiness and MI; whereas DEC is more didactic, and question and answer based. CAMI utilizes open-ended questions, provides advice for change (with permission), and utilizes reflective listening and summaries to elicit a girl's desire, ability, reasons, need and commitment for change.¹⁴ These are integral to MI as used in CAMI, and are not part of the DEC intervention.

Ending Every CAMI & DEC Session. Counselors offered both CAMI and DEC participants a list of community-based locations at which contraceptive services and STI screening can be accessed inexpensively or for free. The counselor recommended that the participant visit her primary care provider or one of the sites on the list for contraceptive supplies, annual pelvic examinations and regular STI screening. Each participant was offered a bag of 2 dozen condoms.

Assessment Procedures and Measurement.

Research staff administered questionnaires using computers. Measures included primary and secondary outcomes (both behavioral and biological), background measures, process measures, and post-intervention assessment. Methods used in this trial to minimize self-report bias included: (1) informing participants that the researchers administering interviews are from the University of Rhode Island; (2) reassuring participants that the information provided is

confidential; (3) using multiple measures of sexual behaviors and contraceptive use through the various questionnaires and TLFB. Biologic samples were utilized and help confirm self-report. As part of participating, girls were asked to provide a release to contact health providers (in order to confirm self-reports).

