Sample size was determined using power analysis for hypothesis tests related to primary aims. Based on the power analysis, a total of 250 teens were to be recruited in order to retain a minimum sample size of about 200 (80% retention) at 9-mo follow-up (FU). Anticipated FU rates were 90%, 85% and 80% at 3-, 6- and 9-mo FU, respectively. These numbers are conservative and are based on comparable recruitment and FU rates as found in the principal investigator’s lab. In probation alone, about 311 female teens per year were placed on probation and about 85% met screening criteria (see above). See Table 1 for the study’s anticipated flow. Youth were recruited from venues on a first come.

Participant Flow:

Year	Baseline	3 Month Follow-Up	6 Month Follow-Up	9 Month Follow-up
1	47	28	10	0
2	72	64	60	48
3	72	63	60	53
4	59	62	60	54
5	0	8	22	45
Total	250	225	212	200

Primary Outcomes (assessed at baseline and follow-ups).

Initiation and Continuous Use of Highly Effective Contraceptives at 3, 6, and 9 Months. A participant switching from one highly effective contraceptive method to another was recorded as maintaining continuous contraceptive use at follow-up if she switched methods during times when the original method was still effective. Use of contraceptive methods was assessed through the TLFB (see below).

Incident STIs. At baseline participants were tested for *T. vaginalis*, *N. gonorrhoeae*, and *C. trachomatis* through self-obtained vaginal swabs. If a participant was diagnosed with an STI at baseline she was to be referred for treatment at a Title X clinic and retested at her next follow-up visit. Any positive test after a baseline negative test was documented as an incident infection. These STIs encompass the most common infections seen in sexually active girls and can result in adverse reproductive sequelae such as infertility, chronic pelvic pain, increased HIV risk and elevated risk of ectopic pregnancy. Other STIs (human papilloma virus, Herpes simplex virus and Syphilis) are not included as the incidence of primary disease in RI is low and diagnosis may require a physical exam or serology.

Secondary Outcomes (assessed at baseline and follow-ups).

Incident Pregnancy. An incident pregnancy was defined as having occurred if there is a baseline negative pregnancy test and a positive urine at follow-up (using a Beta-HCG test) or a self-reported pregnancy confirmed with a positive urine.

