Satisfaction Survey. CAMI and DEC participants completed this 18-item survey of closed and open-ended questions on acceptability of the computerized assessment and counseling. The CAMI participants' survey also contains questions about the perceived fit of the risk assessments for pregnancy and STIs and acceptability of the SAFE plan. All participants completed an abbreviated satisfaction survey at the 9-month follow-up to assess long term satisfaction with the intervention.

Data Analysis.

Sample Size Considerations. Based on the following calculation, we proposed baseline N = 250 subjects.

Specific Aim #1, increasing initiation of highly effective contraception. It is anticipated that CAMI intervention to have a moderate effect on contraceptive initiation rate, resulting in 20% starting a contraceptive method in the treatment group. **Follow-up N = 200 will provide 95% power with a 0.05 two-sided significance level.**

Specific Aim #2, continuation of highly effective contraceptives. Assuming an average within-subject correlation of 0.50, corresponding to a design effect of 2.5, approximately 125 subjects for each group at baseline will provide 80% power for this analysis. In other words, the proposed total sample size of 250 participants at baseline will be enough to achieve excellent

power after considering 20% attrition rate over 9 months (assume continuation increase of 9% for controls and 24% for the intervention group, based on CAMI pilot data).

The secondary outcome of documented pregnancy (Aim 2) will not be powered to detect between group differences. These data are exploratory in nature and inexpensive.

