Missing Data. Because the primary outcome variable, initiation of a contraceptive method, was to be observed for all participants, missing data posed minimal threat to the internal validity of the intervention in determining contraceptive initiation. In the event of item non-response occurring, multiple imputation was to be used to estimate adjusted treatment effects.²⁴ For multiple imputation, 10 data sets were to be generated using SAS Proc MI and the companion procedure PROC MIANALYZE was to estimate the logistic regression model corresponding to analyses for each of the individual aims. If there were differences in the outcomes as a function of missing data pattern, then missing data pattern was to be included as covariate in the analyses.

Literature Cited

1. Guttmacher (2019). Unintended pregnancy in the US. *Fact Sheet*, Guttmacher Institute, NY. Accessed 2-17-23, www.guttmacher.org/fact-sheet/unintended-pregnancy-united-states.
2. Centers for Disease Control (CDC). (2020). Youth risk behavior survey, data summary & Trends report. *National Center for HIV, Viral Hepatitis, STD & TB Prevention, Div of Adolescent & School Health*. Accessed 2-17-23, www.cdc.gov/healthyyouth/data/yrbs/pdf/yrbs_data-summary-trends_report2023_508.pdf
3. DiClemente, R. J., Davis, T. L., Swartzendruber, A., Fasula, A., Boyce, L., Gelaude, D., ...Staples- Horne, M. (2014). Efficacy of HIV/ STI risk reduction intervention for African American adolescent girls in juvenile detention centers. *Women & Health*, 54(8), 726-749. <https://doi.org/10.1080/03630242.2014.932893>
4. Coyle K. K., Franks H. M., Glassman, J. R., & Stanoff, N. M. (2012). Condom use: Slippage, breakage, and steps for proper use among adolescents in alternative school settings. *Journal of School Health*, 82(8), 345-352. <https://doi.org/10.1111/j.1746-1561.2012.00708.x>
5. Brown, L. K., Hadley, W., Stewart, A., Lescano, C., Whiteley, L., Donenberg, G., & DiClemente, R. (2010). Psychiatric disorders & sexual risk among adolescents in mental health treatment. *Journal of Consulting and Clinical Psychology*, 78(4), 590-597. <https://doi.org/10.1037/a0019632>

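### The plan calls missing data a minimal threat to Aim 1 because every girl's initiation outcome will be observed, yet it expects up to 20% loss to follow-up and does not say how lost girls enter the intention-to-treat analysis.

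*Combined protocol and SAP*

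**What the plan says.** The Missing Data section rests Aim 1 on complete observation: "Because the primary outcome variable, initiation of a contraceptive method, was to be observed for all participants, missing data posed minimal threat" to internal validity. It then provides for multiple imputation when items are not answered, with 10 data sets from PROC MI and with PROC MIANALYZE applied to the logistic model for each aim. If outcomes differ by missing-data pattern, the pattern becomes a covariate.

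Other sections bear on whether the premise can be true:

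- **Study Objectives, Aim 1**, on initiation: "This will be measured using calendar-assisted self-report".
- **Primary Outcomes** lists "Initiation and Continuous Use of Highly Effective Contraceptives at 3, 6, and 9 Months" and adds "Use of contraceptive methods was assessed through the TLFB (see below". No visit is named as the one at which initiation is judged.
- **Sample size**: "Anticipated FU rates were 90%, 85% and 80% at 3-, 6- and 9-mo FU, respectively". Recruitment is set at 250 "in order to retain a minimum sample size of about 200 (80% retention) at 9-mo follow-up".
- **Sample Size Considerations, Specific Aim #1**: "Follow-up N = 200 will provide 95% power with a 0.05 two-sided significance level". The CAMI rate is 20%; no DEC rate is given.
- **Assessment Procedures and Measurement**: "girls were asked to provide a release to contact health providers (in order to confirm self-reports".
- **Primary Analyses** promises that everyone randomised is analysed and says differential attrition was assessed. **Contraceptive Initiation (Aim #1)** calls the multiple logistic regression an intent-to-treat analysis.

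**The concern.** Starting a method after counselling can be learned only from a later calendar interview. The baseline assessment precedes both interventions, and the provider releases are there to confirm self-reports, not to replace them. A girl who is never seen again therefore has no Aim 1 outcome, and a girl seen only early has part of one.

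None of the stated provisions clearly covers her. Imputation is tied to item non-response, and the text neither extends it to missed visits and dropout nor rules that out. A pattern covariate cannot supply an absent outcome. Nor can a check for differential attrition, and equal loss in the two arms would not remove bias if the reasons for loss differ between them.

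At stake is the first primary outcome. Its analysis is labelled intention-to-treat on all randomised, but the denominator, the time point and the treatment of lost girls could all be settled after the data are seen.

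**Working it through.** **1. Reproduce the plan's follow-up figures.** 250 × 0.90 = 225; 250 × 0.85 = 212.5 (212 in the flow table); 250 × 0.80 = 200. Not seen: 25 (10.0%), 38 (15.2%) and 50 (20.0%).

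**2. How many girls lack the Aim 1 outcome?** This depends on the time point.

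- Judged at 9 months: 50 of 250.
- Judged at any visit: the visit totals limit those with no follow-up at all to between max(0, 25 + 38 + 50 − 2 × 250) = 0 and min(25, 38, 50) = 25. Those missing at least one visit number between 50 and 25 + 38 + 50 = 113.
- If dropout is monotone (an assumption): 25 have no follow-up, and a further 50 − 25 = 25 are observed only in part. A girl who initiated before leaving has a known outcome.

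**3. A control rate for illustration.** Aim 1 states none, so I solved for the rate that fits the stated power, using a pooled z test with 100 per arm, two-sided 0.05 and CAMI at 20%. A DEC rate of 3.75% gives 95.0% and 4% gives 94.2%. I use 4%, as an assumption.

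**4. Effect on the result with 25 lost per arm.** This is the N = 200 case. It assumes equal loss, 125 randomised per arm, and no use of earlier visits for girls absent at 9 months. The test is z = (p₁ − p₂) / √[p̄(1 − p̄)(2/n)].

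| Handling of lost girls | CAMI v DEC | Difference | p |
|---|---|---|---|
| Dropped | 20/100 v 4/100 | 16.0 points | 0.0005 |
| Counted as not initiated | 20/125 v 4/125 | 12.8 points | 0.0006 |
| Initiating at observed rates | 25/125 v 5/125 | 16.0 points | 0.0001 |
| 6 DEC, 0 CAMI initiate | 20/125 v 10/125 | 8.0 points | 0.052 |
| 10 DEC, 5 CAMI initiate | 25/125 v 14/125 | 8.8 points | 0.055 |

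For the fourth row, p̄ = 30/250 = 0.12, the standard error is √(0.12 × 0.88 × 0.016) = 0.0411, and z = 0.08/0.0411 = 1.95. A search over every combination of lost initiators shows that no combination with fewer than 6 in DEC loses significance.

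**5. The same with only girls who have no follow-up missing.** Take 25 girls, rounded to 13 per arm. Seen girls give 22/112 v 4/112, p = 0.0002. At least 8 of the 13 lost DEC girls (62%) must have initiated before significance could be lost (8 v 0: 22/125 v 12/125, p = 0.065).

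**6. Formal bounds on CAMI minus DEC at 4%.** These put every lost girl in one arm, and none in the other, as an initiator.

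- 20% loss: 0.16 − (0.032 + 0.20) = −7.2 points, to 0.16 + 0.20 − 0.032 = +32.8 points.
- 10% loss: 0.18 − (0.036 + 0.10) = +4.4 points, to 0.18 + 0.10 − 0.036 = +24.4 points.

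**The case against.** The best case for the plan has four parts.

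- **It is not silent on missing data.** It has imputation for every aim, a conditional pattern covariate and an attrition check. This stands, and it would be wrong to infer that the plan has no missing-data method. The gap is narrower: the trigger for imputation is item non-response, and applying it to girls who were not seen is the reader's extension.

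- **If initiation at any visit counts, the visit totals alone permit no girl to be wholly unobserved.** That is arithmetically true. But the plan speaks of retention, and it powers Aim 1 itself on 200 of 250. A girl seen once and then lost without having initiated is still only partly observed. The premise is unsupported by the plan's figures, even though the exact number affected is not fixed.

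- **The result is not fragile.** A reader might infer that one lost girl could overturn Aim 1. That appears only with a 9% control rate borrowed from the Aim 2 continuation assumptions: 20/100 v 9/100 gives p = 0.027, and one lost DEC initiator against none in CAMI gives p = 0.052. But 9% yields about 60% power at 100 per arm, against the stated 95%, so the documents do not support it as the Aim 1 control rate. Nor does the −7.2 point bound show a likely sign change, since it needs all 25 lost DEC girls and no lost CAMI girl to initiate.

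- **Much of the document is in the past tense and it is dated August 2023.** If the analysis has been run, a rule added now is not prespecified. This stands and is reflected in the fix.

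**Conclusion.** The point holds and should be fixed. The premise that initiation is observed for everyone conflicts with the plan's expected follow-up and with the N on which Aim 1 is powered, and no stated provision clearly gives an outcome to a girl lost to follow-up. Without one, the analysis labelled intent-to-treat becomes an analysis of girls with follow-up.

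The harm is possible bias and an open denominator. A likely reversal is not shown. In the N = 200 case at an assumed 4% control rate, 6 of 25 lost DEC girls (24%, six times the rate among those seen) would have to initiate with none in CAMI. If lost CAMI girls initiate at their arm's 20%, 10 of 25 in DEC would be needed. If lost girls initiate at the observed rates, the conclusion is unchanged. These figures rest on equal loss by arm, unadjusted tests and the back-solved control rate. The N = 200 case also sets aside 3- and 6-month data that the plan collects, so it is the less favourable reading.

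**What to change.** 1. Delete the premise that initiation is observed for all participants.
2. State the time point at which initiation is judged.
3. Use the TLFB calendar up to last contact, so that a girl who initiated before leaving counts as an initiator.
4. Extend the planned PROC MI/MIANALYZE step to missed visits and dropout, with arm, baseline contraceptive use and earlier follow-up results in the imputation model.
5. Report two sensitivity analyses: one counting lost girls as not initiated, and one with arm-specific departures from missing at random. They are needed because, for girls with no follow-up at all, imputing from the same baseline covariates adds little to a complete-case logistic regression.
6. If the Aim 1 analysis has already been run, label these additions post hoc.

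The cost is revised wording, some programming with procedures already planned, and possibly slightly wider intervals. No extra participants or visits are needed.

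### Ten imputations are valid, but leave a p-value near 0.05 dependent on the random seed; 100 with a stated seed is a free improvement

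*Combined protocol and SAP*

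**What the plan says.** Four parts of the combined protocol and SAP bear on this.

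- **Data Analysis, Missing Data.** The trigger is item-level: "In the event of item non-response occurring, multiple imputation was to be used to estimate adjusted treatment effects". The number is fixed: "For multiple imputation, 10 data sets were to be generated using SAS Proc MI". PROC MIANALYZE then pools "the logistic regression model corresponding to analyses for each of the individual aims". No seed, Monte Carlo error criterion or FMI is given. The same section expects little missingness for Aim 1: "Because the primary outcome variable, initiation of a contraceptive method, was to be observed for all participants".
- **Sample size (under Selection).** Visit loss is expected: "Anticipated FU rates were 90%, 85% and 80% at 3-, 6- and 9-mo FU, respectively". Enrolment of 250 is meant to "retain a minimum sample size of about 200 (80% retention) at 9-mo follow-up".
- **Sample Size Considerations.** For Aim 1, "Follow-up N = 200 will provide 95% power with a 0.05 two-sided significance level". For Aim 2, "approximately 125 subjects for each group at baseline will provide 80% power for this analysis", with 20% attrition taken into account.
- **Primary Analyses.** All randomized participants are to be analysed, and tests are two-sided at 0.05. Aim 3 is assigned a generalized linear mixed model, with procedures like those for Aim 2.

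**The concern.** Ten imputations estimate the between-imputation variance on only 9 degrees of freedom, and the pooled estimate itself carries simulation noise. Both feed into the p-value that is compared with 0.05. If a primary result lands near that threshold, a second analyst who follows the same plan on the same data with a different seed could report the opposite conclusion. The plan contains nothing that limits this, and nothing that would let a reader see how large the noise was.

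**Working it through.** **Reproduce the plan's figures.** 200 / 0.80 = 250 enrolled. 250 × 0.90 = 225, 250 × 0.85 = 212.5 and 250 × 0.80 = 200, which agree with the participant flow totals of 225, 212 and 200. Planned visit loss is therefore 10%, 15% and 20% at 3, 6 and 9 months.

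**Inputs.** m = 10 (Missing Data); two-sided 0.05 (Data Analysis). FMI is an assumption, shown over a range: 5% as a stand-in for item non-response (the documents give no rate), and 10%, 15% and 20% to match the visit losses.

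**Efficiency.** Relative efficiency is 1 / (1 + FMI/m). At FMI 0.20 and m = 10 this is 1 / 1.02 = 0.98.

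**Approximate size by hand.** Scale the total variance with unlimited imputations to 1, so that the between-imputation variance B equals FMI. The pooled z then varies over seeds with standard deviation √(FMI/m).
- FMI 0.20, m = 10: √0.02 = 0.141, so 95% of seeds put z within 1.96 ± 0.277, that is 1.683 to 2.237. On a normal reference p runs from 0.025 to 0.092.
- FMI 0.20, m = 100: √0.002 = 0.045, so z lies within 1.96 ± 0.088, and p runs from 0.041 to 0.061.

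**Full calculation.** This adds the noise in the variance estimate and the t reference: pooled estimate ~ N(1.96, FMI/m); B̂ ~ FMI × χ²(m−1)/(m−1); W = 1 − FMI; T = W + (1 + 1/m)B̂; r = (1 + 1/m)B̂/W; degrees of freedom (m−1)(1 + 1/r)². With 400,000 draws per setting, the central 95% of reported p-values when the exact p is 0.05 is:

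| FMI | m = 10 | m = 50 | m = 100 |
|---|---|---|---|
| 5% | 0.036–0.071 | 0.043–0.058 | 0.045–0.056 |
| 10% | 0.030–0.084 | 0.040–0.063 | 0.043–0.059 |
| 15% | 0.026–0.096 | 0.038–0.067 | 0.041–0.061 |
| 20% | 0.023–0.109 | 0.036–0.070 | 0.039–0.064 |

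**Change of conclusion at FMI 20%.** An exact p of 0.03 is reported as non-significant for about 16% of seeds at m = 10, 0.4% at m = 50 and under 0.1% at m = 100. An exact p of 0.07 is reported as significant for about 16%, 2% and 0.2%. At FMI 5% and m = 10, an exact p of 0.03 changes side for only 0.4% of seeds.

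**Check without the normal model.** A binary outcome was imputed directly, with 125 per arm, 25 per arm missing and no auxiliary variables. This gave an FMI of about 0.195. An exact p of 0.046 ranged over 0.022–0.101, and an exact p of 0.052 over 0.025–0.112. Both agree with the 20% row.

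**The case against.** The strongest objection is that the plan does not say it imputes the loss it expects. The trigger is item non-response, whereas the 10% to 20% figures are missed visits. The same section also says initiation is observed for all participants. A reader might infer that ten imputations are too few for the planned 20% loss, and that any primary p-value of 0.05 could come out anywhere from 0.02 to 0.11. The documents do not support that. The range covers 95% of seeds, not every seed. It needs FMI 20%, which no document states and which assumes that earlier visits and covariates recover nothing. On the plan's own wording, Aim 1 would depend very little on the seed. The mixed model for Aim 3 can also use all observed visits without imputation.

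This stands, with one limit. The scope of imputation is not settled by the text: Aim 1 is powered on a follow-up N of 200, which sits badly with initiation being observed for all 250. All randomized participants are to be analysed, and imputation is said to serve the models of every aim. Imputing missed visits is therefore possible, most plausibly for the 3-, 6- and 9-month outcomes of Aims 2 and 3. Raising m does not resolve that ambiguity.

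A second objection is that the effect matters only near the threshold. This also stands. Over all possible results with m = 10, two analysts with different seeds would disagree at 0.05 in 2.4% (FMI 5%), 3.6% (10%) or 5.8% (20%) of trials at 80% power, and in about 1% to 2% under the null. Rubin's rules allow for finite m: type I error stays at about 0.05, and power falls from 80% to about 78.7% at worst.

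**Conclusion.** The point holds as a minor matter of reproducibility. It is not a fault of validity: there is no bias and no inflated type I error. With ten imputations, a result whose exact p is 0.05 would be reported between 0.036 and 0.071 for 95% of seeds at FMI 5%, which is closest to the plan's wording. At FMI 20%, the upper case, the range is 0.023 to 0.109. All of this rests on assumed FMI values. It is of little consequence for Aim 1 if initiation really is observed for everyone, and of more consequence for Aims 2 and 3 if missed visits are imputed. Results well away from 0.05 are unaffected in practice. It is best labelled a free improvement.

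**What to change.** In the Missing Data section, replace 10 by 100 imputed data sets (at least 50), which is NIMPUTE=100 in PROC MI. Pre-specify the seed, and report the Monte Carlo error of the treatment estimate beside its standard error. A fixed seed alone makes a rerun repeatable but leaves the noise in place; the larger m removes most of it. In the same edit, state whether imputation covers missed visits or only item non-response. If the analyses have already been run, rerun the imputed models with the larger number and report the Monte Carlo error. The cost is one number, two added statements and slightly more computing time at N = 250.

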Specific Aim #3, decrease in unsafe sexual activity, the primary outcome is incident STIs. The following is assumed: Type I error of $\alpha=.05$, an average within-subject correlation of 0.50 and 20% attrition rate. Using similar procedures as above, the proposed enrollment of 250 participants at baseline will achieve power of 80% to detect differences after considering 3 repeated measures (3, 6, 9 months). For the secondary outcome in Specific Aim #3, decrease in unsafe sexual activity, the following is assumed: Type I error of $\alpha=.05$, an average within-subject correlation of 0.50 and 20% attrition rate. Using the similar procedure as above, the proposed enrollment of 250 participants at baseline will achieve power of 97% to detect assumed differences. The proposed sample size may provide greater power to detect interaction effects, robustness to violations of model assumptions, protection against multiple comparison error rates, and increase efficiency to detect weaker relationships between variables.

Descriptive Analysis. Initially, descriptive statistics were used to summarize the variables as well as detect outliers, data entry mistakes, and missing values. Effectiveness of the randomization procedures was assessed through comparison of the two treatment arms on all baseline measures. Comparisons of baseline characteristics used Student's t-test, and Chi-square test. Data analyses were performed using "Statistical Analysis Software" (SAS Institute, Inc, Cary, North Carolina). All significance tests will be two-tailed.

Primary Analyses. Following intention-to-treat principles, all participants who have been randomized to the two conditions will be included in the analyses. Differential attrition across treatment groups was not expected, but this unlikely occurrence was assessed.

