Contraceptive Initiation (Aim #1). Analyses of contraceptive initiation included the percentage starting a highly effective method (DepoProvera or an IUD) and highly effective methods requiring regular non-coital use (contraceptive pills, vaginal rings, the patch etc). This intent-to-treat analysis used multiple logistic regression to determine if girls randomized to the CAMI condition were more likely to initiate a contraceptive method than girls randomized to the DEC condition. The background characteristics (age, gender, race) or baseline characteristics (e.g., pregnancy related variables, and contraceptive history) and some meaningful interaction terms will be incorporated in the initial full model. All the p values are calculated with two-sided significance level of 0.05. Odds ratios and their 95% confidence intervals will be calculated for any important explanatory variables.

Contraceptive Continuation (Aim #2). Testing interactions between treatment and time illuminated whether differences in contraceptive outcomes between treatment conditions became more or less pronounced over the 9 months of follow-up.

Incident STIs (Aim #3). All STIs tested through the study were evaluated. Generalized linear mixed model (GLMM) were used to test this hypothesis, and procedures similar to those outlined in Aim #2 were used.

Secondary Analyses (Aim #2 and Aim #3). The following were utilized 1) pregnancy incidents and 2) the TLFB to identify the percentage of at-risk-days that girls engage in unprotected sexual activity. GLMM was used to test this hypothesis, and procedures similar to those outlined in Aim #2 will be followed.

Predictors of contraceptive use. These included demographics of age, race/ethnicity and education as well as drug and alcohol use, recent and childhood victimization and pregnancy history. Measurement modeling was used to incorporate multiple measures, such as the self-reported primary outcomes and the incidence of pregnancy and STD in a latent factor that captures variance common to all measures²⁴.

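### Adding the missing-data pattern as a covariate can move the Aim 2 and 3 arm effects away from intention-to-treat if outcome-related loss differs by arm

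*Combined protocol and SAP*

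**What the plan says.** The combined protocol and SAP treats missing data in one short paragraph, Missing Data, which makes three statements.

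- Aim 1 is expected to be complete: "Because the primary outcome variable, initiation of a contraceptive method, was to be observed for all participants".
- Imputation is tied to unanswered items: "In the event of item non-response occurring, multiple imputation was to be used to estimate adjusted treatment effects". Whole missed visits are not named.
- The pattern rule is conditional. It applies if outcomes differ "as a function of missing data pattern, then missing data pattern was to be included as covariate in the analyses". It covers the analyses in general and is not labelled a sensitivity analysis. Neither the pattern nor the test for a difference is defined.

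Elsewhere, Primary Analyses sets the population: "Following intention-to-treat principles, all participants who have been randomized to the two conditions will be included in the analyses". It adds that unequal attrition was not expected but was assessed, and states no consequence if it is found. For Aim 3 the model is named: "Generalized linear mixed model (GLMM) were used to test this hypothesis". The secondary outcomes use the same class of model, and Aim 2 tests treatment-by-time interactions. The Sample size section gives the planned loss: "Anticipated FU rates were 90%, 85% and 80% at 3-, 6- and 9-mo FU, respectively".

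**The concern.** Who is lost, and when, is settled after randomization and may depend on the arm. The rule comes into force exactly when the pattern is related to outcome. If the arm also affects that loss, adjusting for pattern conditions on a consequence of treatment that is associated with the outcome.

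A repeated-measures model on all observed visits, without pattern, lets the earlier visits of girls who later leave inform their missing visits through the within-girl correlation. It is valid, if correctly specified, when dropout depends on earlier observed use. A pattern main effect absorbs that information and leaves a comparison of arms among girls with the same follow-up history. A valid pattern-mixture estimate would allow the arm effect to differ by pattern and then average over each arm's own pattern frequencies. The plan describes neither step.

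What is at stake is the arm effect on continuation, incident STIs and the secondary outcomes. The shift could favour either arm.

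**Working it through.** **1. The plan's attrition figures.** From Sample size: 250 × 0.90 = 225; 250 × 0.85 = 212.5 (212 in the flow table); 250 × 0.80 = 200. These reproduce.

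**2. How much of the follow-up comes from completers.** The documents do not say whether loss is monotone.

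- If it is monotone, 250 − 225 = 25 girls have no follow-up, 225 − 212 = 13 have one visit, 212 − 200 = 12 have two, and 200 have three. Planned visits total 225 + 212 + 200 = 637. Completers supply 3 × 200 = 600, and 600/637 = 94%.
- At the other extreme, every missed visit belongs to a different girl. Missed visits are 25 + 38 + 50 = 113, completers are 250 − 113 = 137, and they supply 3 × 137 = 411 visits; 411/637 = 65%.

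The near-completer description therefore rests on loss being mostly monotone.

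**3. What the covariate changes.** With pattern k, the model is logit P(Y = 1) = α + β·arm + visit + γₖ, and β compares arms within a pattern. The intention-to-treat contrast compares Σₖ πₖ,ₐ pₖ,ₐ between arms a, where π is the pattern frequency and p the outcome rate. Under no effect the two agree if the dropout process is the same in both arms, or if loss is unrelated to outcome. Otherwise they need not.

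**4. Size under no true effect (true OR 1.00).** All retention by arm is assumed.

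| Assumed loss | 9-month retention, CAMI / DEC | OR without pattern | OR with pattern |
|---|---|---|---|
| A. Depends on last observed use; DEC loses mainly non-users | 105–106 / 92 of 125 | 0.99–1.00 | 0.90–0.92 |
| B. Same type of loss, larger simulation | about 108 / 91 of 125 | 1.00 | 0.89 |
| B, dropout reversed | reversed | 1.03 | 1.16 |
| B, same process in both arms | same process | 1.01 | 1.01 |
| C. Unrelated to outcome | 85% / 73% | 1.00 | 1.00 |
| D. Driven by an unmeasured factor | 80% / 80% | 1.00 | 1.00 |
| D | 75% / 85% | 1.11 | 1.12 |
| D | 85% / 75% | 0.90 | 0.89 |
| D | 70% / 90% | 1.17 | 1.25 |
| D | 90% / 70% | 0.85 | 0.80 |

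- A: 125 per arm, 10% never seen, 1,200 runs per scenario. The gap is 84.0–84.8% against 73.6%, or 10.4 to 11.2 points.
- B: 40,000 girls per scenario, 10% never seen, standard error of the OR about 0.02. The gap is 86.4% against 72.8%, or 13.6 points.
- C: 400,000 girls.
- D: 1,000,000 girls, three visits, monotone loss, and an outcome rate of 16.5% in both arms, the midpoint of the 9% and 24% in the Aim 2 sample-size text. One shared factor has assumed log-odds slopes of 1.5 on retention and 1.8 on outcome.
- A and B use an exchangeable logistic GEE as a stand-in for the GLMM. D uses a working-independence logistic model.

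**5. Closeness to a completers analysis.** In setting D with rates of 24% and 9%, the true OR is (0.24/0.76)/(0.09/0.91) = 3.19. At 75/85 retention the pattern-adjusted OR is 3.65 and the completers-only OR 3.62. At 70/90 they are 4.04 and 4.01.

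**The case against.** The strongest reply is that the rule is conditional, that the plan did not expect unequal attrition and did assess it, and that no figure in the documents shows a difference between arms. This stands, and it makes the bias potential rather than shown. It does not rescue the rule, because the assessment leads to no stated action and the rule's trigger concerns outcome, not arm.

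Two further points stand. The pattern is undefined and follows sentences about unanswered items, so reading it as dropout wave is an interpretation. And removing the covariate is not a full remedy: when an unmeasured factor drives loss, the null OR is 1.11 without pattern and 1.12 with it. That comparison uses a working-independence model. A mixed model might recover a little more, but no model on observed visits uses girls who were never seen.

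Three stronger readings are tempting, and the documents support none of them.

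- *Unequal retention alone biases the adjusted effect.* It does not: with 85% and 73% retained and loss unrelated to outcome, the OR is 1.00 either way.
- *The rule materially inflates the false-positive rate.* The documents give no retention by arm from which to establish this, and changes in rejection rate in simulations of this size were within simulation noise.
- *The imputed data are analysed by a plain logistic model that ignores repeated visits.* The text says "the companion procedure PROC MIANALYZE was to estimate the logistic regression model corresponding to analyses for each of the individual aims". With a GLMM specified for Aim 3 and the secondary outcomes, the natural reading is a mixed logistic model. The wording is loose for the percentage-of-days outcome, but no plain model on stacked visits is in the plan.

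**Conclusion.** The concern holds as a conditional one. The plan applies a post-randomization covariate to its analyses, and where outcome-related loss differs by arm the result departs from the intention-to-treat effect. When loss depends on earlier observed use, which is the case a model without pattern handles, gaps of about 10 to 15 points move a null OR from about 1.00 to about 0.90, or to about 1.1 to 1.2 in the other direction. That is modest and of unknown sign. It rests on assumed retention by arm, assumed links between use and loss, and the GEE stand-in. Aim 1 is largely out of reach on the plan's own statement that initiation was to be observed for all. Nothing here shows that the trial's results are biased. The change should be made because the rule can do harm and the alternative is cheap.

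**What to change.** - Remove the pattern covariate from the primary models for Aims 2 and 3. Keep the repeated-measures model on all observed visits, without pattern, as primary, and do the same for the secondary outcomes.
- Add one sensitivity analysis that covers whole missed visits. Use either a pattern-mixture model with arm-by-pattern effects averaged over each arm's own pattern frequencies, or delta-adjusted multiple imputation with a tipping point. Define the pattern if the first is chosen.
- Report retention by arm at 3, 6 and 9 months.

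The cost is SAP wording and one extra run, with no new data. If the analyses are already complete, report the arm effects with and without pattern beside the retention figures.
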